3.1 Primary Research Question

Does outpatient cervical ripening with a transcervical Foley catheter shorten the admission to delivery time compared to the standard inpatient transcervical Foley catheter cervical ripening method?

3.2 Secondary Research Aims

- a. To assess patient satisfaction in both groups of patients to determine if patients in the outpatient Foley catheter group have higher satisfaction rates compared to the standard inpatient induction method.
- b. To assess the incidence of adverse outcomes in both groups. This will be evaluated by vaginal bleeding greater than bloody show, intractable pain requiring early admission in the outpatient (intervention) group, intractable pain requiring epidural placement while the Foley bulb remains in situ, nonreassuring fetal heart rate tracings upon admission in the outpatient group, and nonreassuring fetal heart rate tracing prompting immediate delivery.
- c. To assess the incidence of the following:
 - a. Outpatient group presenting to the Maternity Evaluation Unit (MEU) prior to their scheduled admission time.
 - b. Outpatient group having spontaneous rupture of membranes (SROM) prior to their scheduled admission time.
 - c. Chorioamnionitis or endometritis in each group.
- d. To assess the total time of epidural use in each group.
- e. To compare the mode of delivery between the two groups.
- f. To assess the following oxytocin parameters between the two groups.
 - a. Total time of infusion.
 - b. Total cumulative dose of oxytocin infused.
 - c. Maximum rate (milliunits/min) of oxytocin infused.
- g. To compare labor and delivery charges between the two groups.
- h. To assess a composite neonatal outcome between the two groups based on the following parameters:
 - a. Apgar score < 7 at 5 minutes
 - b. Arterial cord blood gas pH < 7.1
 - c. Arterial cord blood gas base deficit > -12
 - d. Admission to the neonatal intensive care unit.

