1.2 Secondary Hypotheses

- a. Patients in the outpatient group will have higher satisfaction scores than those undergoing cervical ripening in the inpatient setting.
- b. The following hypotheses pertain to the incidence of the following events:
 - a. Outpatient cervical ripening will not increase the incidence of adverse outcomes compared to inpatient cervical ripening. Based on prior studies evaluating the safety of the transcervical Foley catheter, we do not anticipate there to be heavy vaginal bleeding, immediate need for delivery for a non-reassuring fetal heart tracing, or stillbirths in either group.
 - b. A small number of patients in the outpatient transcervical Foley catheter group will require admission prior to their scheduled arrival time because of intractable pain from the transcervical Foley catheter. Additionally, a small number of patients will require an epidural for pain control while the Foley catheter remains in situ.
 - c. Immediate delivery for non-reassuring fetal heart rate tracings after placement of the transcervical Foley catheter will not be required in either group.
 - d. A small number of patients in the outpatient transcervical Foley catheter group will present to the Maternity Evaluation Unit (MEU) for evaluation prior to their scheduled admission time.
 - e. Spontaneous rupture of membranes (SROM) will occur at similar rates in the two groups.
 - f. Outpatient cervical ripening with the Foley catheter will not increase infectious morbidity as compared to inpatient cervical ripening.
- c. Epidural usage, and thus immobilization, will be higher in the inpatient group compared to the outpatient group.
- d. The outpatient and inpatient groups will have similar rates of vaginal and cesarean deliveries.
- e. The following hypotheses pertain to oxytocin usage between the two groups:
 - a. The inpatient group will require longer duration of oxytocin infusion, higher cumulative doses, and higher maximum rates than the outpatient transcervical Foley catheter group.
- f. The outpatient group will have lower labor and delivery charges than the inpatient group.

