2.4 Safety of outpatient induction of labor

There is limited data on outpatient cervical ripening, and thus, this prompted authors of a Cochrane review (Kelly et al 2013) to conclude there was not sufficient evidence to establish the safety of cervical ripening in the outpatient setting. Sciscione et al (2014) created a theoretical cohort of outpatient transcervical Foley catheter for cervical ripening and reviewed labor and delivery as well as neonatal outcomes in over 1900 women. This "low-risk" cohort excluded patients with gestational hypertension, preeclampsia, multiple gestations, pregestational diabetes, and stillbirth, and found no adverse events in the group. There were not any cases of placental abruption or stillbirths. Only 2/1905 had an emergent cesarean section after placement of the transcervical Foley catheter for non-reassuring fetal heart rate tracings during the immediate postplacement monitoring. Only 3/1905 required a cesarean section for non-reassuring fetal heart rate tracings during the theoretical "outpatient" time period.

We have reviewed 43 consecutive privately insured cervical ripening admissions at the University of Alabama at Birmingham. In this cohort, transcervical Foley catheters were placed without initiation of oxytocin. There were not any placental abruptions, non-reassuring fetal heart rate tracings necessitating delivery, or stillbirths between placement of the transcervical Foley catheter and the next morning, which represented a theoretical "outpatient" time period.

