- e. If the Foley catheter is unable to be placed secondary to the patient not being dilated enough to pass the catheter through the cervix, the patient will be asked to return in 24-72 hours later to again attempt placement of the Foley catheter. If the cervix is closed, there is a higher chance of a failed induction and cesarean section with proceeding with the induction of labor.
- f. As is standard in our practice, oxytocin will be initiated concurrently, and the fetal heart rate will be continuously monitored per protocol. The patient will remain NPO.
- g. A nurse or physician will assess the Foley bulb every 2-4 hours with gentle traction. It may be re-taped at this point.

c. Group 2 (Intervention)

- a. The transcervical Foley catheter will be placed in the exact manner as described in the above group 1 (standard treatment) description.
 - i. As the cervix effaces and dilates (aka ripens), it is normal to have a small amount of bleeding. Since this is a Foley catheter designed for use of draining urine from the bladder, the end of the catheter can drain a small amount of blood.
 - ii. If the Foley catheter is unable to be placed secondary to the patient not being dilated enough to pass the catheter through the cervix, the patient will be asked to return in 24-72 hours to again attempt placement of the Foley catheter. If the cervix is closed, there is a higher chance of a failed induction and cesarean section with proceeding with the induction of labor.
- b. The patient will undergo 30 more minutes of fetal monitoring and be discharged home if it is Category I. ‡
- c. The patient will then be given a sheet containing important information regarding reasons to present to the hospital prior to the scheduled induction the next morning. Importantly, the direct physician 24-hour triage line (MEU) will be clearly listed on the paper.
 - i. Reasons to return to the hospital or call the physician include:
 1. Standard labor precautions (decreased fetal movement, concern for rupture of membranes or contractions every 5 minutes for one hour)
 2. Uncontrolled pain, and/or vaginal bleeding soaking a pad or their underwear.

- ii. Patients will be instructed that a small amount of vaginal bleeding is to be expected as well as it is normal for the Foley catheter to be expelled as the cervix ripens.
 1. Thus, patients will be instructed to record the time of expulsion and report for their induction as scheduled unless any of the aforementioned conditions exist.

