4.8.2. Secondary outcomes

- a. Patient satisfaction
- b. Placental abruption
- c. Early admission for intractable pain (outpatient group)
- d. Intractable pain requiring epidural anesthesia while the transcervical catheter remains in situ
- e. Non-reassuring fetal heart rate tracing upon admission in the outpatient group
- f. Non-reassuring fetal heart rate tracing while the transcervical catheter remains in place requiring immediate delivery
- g. MEU visits prior to scheduled admission time (outpatient group)
- h. SROM occurring in the outpatient group prior to scheduled admission time
- i. Chorioamnionitis or endometritis
- j. Total time of epidural use
- k. Mode of delivery
- l. Total time of oxytocin infusion
- m. Total cumulative dose of oxytocin infused
- n. Maximum rate (milliunits/min) of oxytocin infused
- o. Labor and delivery charges
- p. Composite neonatal outcomes
 - a. Apgar score < 7 at 5 minutes
 - b. Arterial cord blood gas pH < 7.1
 - c. Arterial cord blood gas base deficit > 12

- d. Admission to the neonatal intensive care unit.

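### The safety aim calls for a bleeding outcome, but the outcome list has no bleeding item and lists placental abruption in its position

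*Combined protocol and SAP*

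**What the plan says.** Three sections bear on bleeding as an outcome, and they differ.

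- **1.2 Secondary Hypotheses, b.a:** "we do not anticipate there to be heavy vaginal bleeding" in either group.
- **3.2 Secondary Research Aims, b:** the incidence of adverse outcomes is to be assessed in both groups. The first measure named is "vaginal bleeding greater than bloody show", followed by two pain items and two fetal-tracing items. Abruption is not mentioned.
- **4.8.2 Secondary outcomes:** after satisfaction comes "Placental abruption", then the same pain and tracing items. None of items a to p is a bleeding outcome.

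Other sections matter for how bleeding would be recorded. Section 3.6 tells outpatients to call or return for "vaginal bleeding soaking a pad or their underwear", and that a little bleeding is to be expected. Section 4.6 takes outcomes from the charts and describes the postpartum surveys as covering satisfaction. Section 4.7 already lists abruption among the serious adverse events.

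**The concern.** An abstractor working from 4.8.2 would collect abruption and no bleeding outcome, so a safety aim stated for both arms would have no data behind it. The expectation about heavy bleeding in 1.2 would have no listed outcome either. Abruption is a distinct diagnosis. A woman can bleed more than bloody show without it, and a count of zero abruptions says little about how often that happens.

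Following 3.2 does not settle the matter, because the plan does not say how bleeding at home would be recorded. The arms differ in who observes the woman during ripening, so a count from charts alone may not be comparable. This matters because section 6 makes a multicentre follow-on depend on showing that outpatient placement is safe and well tolerated.

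**Working it through.** **Step 1. The two lists side by side.**

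| Position | Aim 3.2 b | List 4.8.2 |
|---|---|---|
| 1 | Bleeding above bloody show | Abruption (item b) |
| 2 | Early admission for pain, outpatients | Same (item c) |
| 3 | Epidural for pain, catheter in place | Same (item d) |
| 4 | Fetal tracing at admission, outpatients | Same (item e) |
| 5 | Fetal tracing leading to immediate delivery | Same in substance (item f) |

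Only the first position differs. Both are current text, and no section defines abruption as a measure of bleeding.

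**Step 2. The denominator.** Section 5.1 gives SD 24 h, difference 12 h, two-sided alpha 0.05 (the test is two-sided in 5.3) and power 80%. The normal approximation is n = 2 × (1.96 + 0.842)² × (24/12)² = 62.8, so 63 per group. The t-test version gives 63.8, so 64, with power 0.801. The plan's 64 per group reproduces, for a total of 128.

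**Step 3. How many abruptions to expect.** Section 2.4 says of the cited cohort: "There were not any cases of placental abruption or stillbirths". The denominator, 1905, appears in the same section ("Only 2/1905 had an emergent cesarean section after placement of the transcervical Foley catheter").

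- Two-sided 95% upper limit: 1 − 0.025^(1/1905) = 0.193%. Expected events: 128 × 0.00193 = 0.25. Chance of none: (1 − 0.00193)^128 = 0.78.
- One-sided 95% upper limit: 1 − 0.05^(1/1905) = 0.157%. Expected events: 0.20. Chance of none: 0.82.
- Predictive chance of none with a uniform prior: 1906/(1906 + 128) = 0.94.

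With no event in either arm, the chi-square test and relative risk planned in 5.4 cannot be calculated. A count of 0/64 in one arm still leaves a one-sided 95% upper limit of 1 − 0.05^(1/64) = 4.6%.

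**Step 4. What a bleeding outcome could show.** The documents give no rate for bleeding above bloody show, so the rates below are assumptions.

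| Assumed rate | Expected events in 128 | Chance of none | Power to detect a doubling, 64 per group |
|---|---|---|---|
| 1% | 1.3 | 28% | 7% |
| 5% | 6.4 | 0.1% | 19% |
| 10% | 12.8 | below 0.001% | 35% |
| 20% | 25.6 | below 0.001% | 70% |

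Unless the rate is near the bottom of this range, some events would probably be seen. Power stays below 80% throughout, so the outcome supports description rather than a test.

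**Step 5. Which bleeding the charts would catch.** For outpatients, 3.6 provides several routes into the record: the instruction to call or return, direct admission for significant bleeding after placement, and a routine assessment on arrival the next morning. Early visits to the evaluation unit are item g in 4.8.2. What may be lost is bleeding above bloody show but below the return threshold, or bleeding on which the woman did not act. Nothing requires staff to ask about it on arrival. For inpatients, 3.6 has a nurse or physician check the catheter every 2 to 4 hours, so there is regular opportunity to notice bleeding.

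**The case against.** The strongest reply is that the plan's safety assessment does not rest on this line, and that is right. Section 4.8.2 keeps pain, fetal tracings, unscheduled visits, membrane rupture, infection and a neonatal composite. Section 4.7 adds serious-event reporting and a safety board. A reader might infer that the list leaves abruption as the only safety outcome; the documents do not support that. That one item was deliberately substituted for the other is likewise only an inference from list position. What the text shows is two unreconciled lists.

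A reader might also infer that the abruption count is all but certain to be zero. The 94% predictive figure leans that way, but at the upper limit the chance of none is 78%, and a confidence limit is not a ceiling. The cohort was a theoretical outpatient one and 4.8.2 sets no time window for abruption, so the rate may not carry over. Expecting no events is also not a defect in itself: 1.2 expects no heavy bleeding.

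Finally, a reader might infer that bleeding at home is simply missed. The routes in step 5 rule that out for bleeding that prompts a call, visit or admission, and the arrival assessment could bring out more. Nor do the documents say that every inpatient's bleeding is seen, or charted against this threshold. The direction of bias is plausible but not shown.

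None of this supplies the missing item. An aim to assess incidence needs the outcome collected, even where 5.2 concedes limited power.

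**Conclusion.** The inconsistency stands. Aim 3.2 b requires a bleeding outcome in both arms, 4.8.2 does not contain one, and abruption cannot answer for it. At the two-sided 95% upper limit from the cited cohort, about 0.25 abruptions would be expected in 128 women, with a 78% chance of none. This assumes that the cohort's rate applies to this trial and its follow-up period.

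If 4.8.2 is followed, the bleeding aim is not answered. If bleeding is taken from charts alone, under-recording of moderate bleeding at home would plausibly favour the outpatient arm. Its size is unknown, because the documents give neither a bleeding rate nor a charting rule.

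The primary outcome, its analysis and the sample size are unaffected. This is a modest point, but worth settling in advance, since bleeding at home that nobody asked about cannot be recovered from a chart later.

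**What to change.** - **Reconcile 1.2, 3.2 and 4.8.2.** Add bleeding above bloody show to 4.8.2, with one outcome definition for both arms, and use it in all three sections. A threshold set only at heavy bleeding would bring back an outcome that 1.2 expects not to occur.
- **Set a comparable ripening-period window in both arms.** For outpatients it should run from placement, or attempted placement, through admission, and include time at home after expulsion. A window ending at expulsion would leave out unobserved hours, since 3.6 treats expulsion at home as normal. Starting at attempted placement covers women whose catheter could not be placed (4.3 and 4.4), in keeping with intention to treat.
- **Record it the same way.** Ask every outpatient a standard question at the admission assessment, and record the same item for inpatients during ripening. A question left to the postpartum survey risks mixing ripening-period bleeding with bleeding in labour or at delivery.
- **Keep abruption as a separate item.** Report bleeding descriptively, as counts and proportions with confidence intervals, because power is limited.

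The cost is one data item and one question. The sample size does not change, and neither do the clinical return instructions: the outcome definition is for recording only.

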- g. Outpatient cervical ripening will not increase the risk of adverse neonatal outcomes compared to inpatient cervical ripening, as assessed by a composite neonatal outcome. This composite neonatal outcome measure will include Apgar score < 7 at 5 minutes, arterial cord blood gas pH < 7.1, arterial cord blood gas base deficit or excess < -12, and/or admission to the neonatal intensive care unit.

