4.6 Participant follow-up

Patients will be followed-up once during their postpartum inpatient hospitalization. This follow-up will be done post-delivery and before their discharge and will include a short series of surveys evaluating patient satisfaction regarding inpatient and outpatient cervical ripening. Investigators and principal investigators experienced in abstracting obstetrical and perinatal outcomes will review the patients' and neonates' charts after delivery to abstract the necessary variables to satisfy the primary and secondary outcomes. No further patient follow-up will occur after discharge from the UAB Women and Infants Center.

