4.8 Study Outcome Measurements and Ascertainment

4.8.1. Primary outcome

The primary outcome is the time from admission to delivery.

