4.8.3. Follow-up and Outcome Ascertainment Periods

The primary outcome will be ascertained by recording the time of admission and delivery listed in the electronic medical record. The total length of time will be computed in minutes. Follow-up will occur during the postpartum period prior to maternal discharge. Neonatal information will be collected from the neonate's electronic medical record.

5. Statistical Considerations

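### Section 3.2 gives the base-deficit part of the neonatal composite the wrong sign, in conflict with Section 4.8.2, and no sign convention is stated

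*Combined protocol and SAP*

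**What the plan says.** The composite appears in three places in the combined protocol and SAP. The Apgar, cord pH and intensive-care components are the same each time. Only the base-deficit component changes:

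- Section 1.2, item g: "arterial cord blood gas base deficit or excess < -12"
- Section 3.2, item h.c: "Arterial cord blood gas base deficit > -12"
- Section 4.8.2, item p.c: "Arterial cord blood gas base deficit > 12"

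Section 1.2 names the composite as the measure for the hypothesis that "Outpatient cervical ripening will not increase the risk of adverse neonatal outcomes". It joins the last component with "and/or admission to the neonatal intensive care unit", which implies that any one component makes the composite positive. Section 5.4 compares event outcomes by chi-square test and relative risk, so each newborn must be classed as positive or negative.

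On data capture, Section 4.8.3 says "Neonatal information will be collected from the neonate's electronic medical record". It does not say whether the value is recorded as deficit or as excess, or with which sign.

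**The concern.** Base deficit and base excess are the same quantity with opposite signs, so a threshold has meaning only once the quantity and its sign are fixed. Section 3.2 names a deficit but attaches a negative cut-off with a greater-than sign. That does not isolate acidotic newborns under either convention. Section 1.2 puts both names under one negative cut-off, which works only if the value is read as base excess.

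The composite is the stated neonatal safety measure. If Section 3.2 were applied literally, with any component counting, the composite would be positive for nearly every newborn with a cord gas in both arms. It would then mainly record whether a gas had been taken, and could not serve as a safety comparison. A quieter slip is also possible: the Section 4.8.2 rule could be applied to a chart value stored as -14, and the component would be missed.

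**Working it through.** **Inputs.** The three wordings above, and the identity base excess = -(base deficit). The documents give no event rate, cord-gas sampling rate or power for the composite, so there is no planned figure for it to reproduce. The only sample-size figure is the 64 per group in Section 5.1. It reproduces (12-hour difference, SD 24 hours, two-sided alpha 0.05, 80% power: 63.77 by the t-test, rounded up to 64) and does not depend on this point.

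**Two example newborns.** A has deficit 5 (base excess -5). B has deficit 14 (base excess -14). The intended rule should flag B and not A.

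| Wording | Value used | A | B |
|---|---|---|---|
| 4.8.2: > 12 | positive deficit | 5 > 12: no | 14 > 12: yes |
| 1.2: < -12 | base excess | -5 < -12: no | -14 < -12: yes |
| 3.2: > -12 | positive deficit | 5 > -12: yes | 14 > -12: yes |
| 3.2: > -12 | negative value | -5 > -12: yes | -14 > -12: no |
| 1.2: < -12 | positive deficit | 5 < -12: no | 14 < -12: no |
| 4.8.2: > 12 | negative value | -5 > 12: no | -14 > 12: no |

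Of the six combinations, two give the intended result. Two, both from Section 3.2, flag the newborn without acidosis. Two flag neither newborn.

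**Check over a range.** The same rules were applied to deficits from -5 to 25 in steps of 0.1. That is 301 values, of which 130 exceed 12 and 171 do not. The grid tests logic and is not a distribution of newborns. The reference is Section 4.8.2 on positive deficit.

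- Section 3.2 on positive deficit flags 301 of 301, including all 171 at or below 12.
- Section 3.2 on negative values flags the 170 values below 12 and none of the 130 above. It agrees with the reference only at exactly 12.0, where neither rule is met.
- Section 1.2 read as base excess agrees with the reference at 301 of 301.
- Section 1.2 on positive deficit flags 0 of 301.
- Section 4.8.2 on negative values flags none of the 130.

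**Illustration under assumed distributions.** For scale only, deficit was taken as normal with four assumed (mean, SD) pairs: (3, 3), (4, 3), (5, 4) and (6, 4). The share above 12 is then 0.13%, 0.38%, 4.0% and 6.7%. The share above -12 is at least 99.99% in each case. The share flagged by Section 3.2 on negative values is 99.87%, 99.6%, 96.0% and 93.3%. These inputs are assumptions and do not come from the documents.

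**Which wording is the outlier.** Sections 4.8.2 and 1.2 have one reading on which they agree everywhere. Neither literal reading of Section 3.2 agrees with them.

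**The case against.** The strongest reply is that the plan already contains the right rule where it belongs. Section 3.2 is a list of aims. The definition sits under "Study Outcome Measurements and Ascertainment", and there it is coherent. Charts are to be abstracted by "Investigators and principal investigators experienced in abstracting obstetrical and perinatal outcomes", who would hardly flag every newborn. Section 3.2 may also be loose shorthand for a value worse than -12, in which case all three sections mean the same thing. Section 1.2 can be read as naming one signed laboratory value, which is coherent. Naming a deficit with a positive cut-off in Section 4.8.2 arguably implies the sign. The stored-as-negative slip is conjecture, since no section says how the record holds the value, and such a newborn might still count through pH, Apgar score or intensive-care admission.

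Much of this stands. Literal use of Section 3.2 is unlikely. The last two rows of the table are better called abstraction errors than readings of the text. Rewording Section 1.2 is tidying more than correction. What does not stand is the shorthand reading as a defence: it is not what the inequality says, and a rule that classes each newborn cannot rest on it. Experience lets an abstractor infer the intent, but it does not put one definition in writing.

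**Conclusion.** The point holds and is minor. The criterion in Section 3.2 is wrong as written under either sign convention, and it contradicts Section 4.8.2 and the workable reading of Section 1.2. It is most likely a typographical error, since all three places use the number 12 and the intended rule can be recovered from the outcome section.

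The conclusion rests on sign logic and needs no event rate. That practically every newborn with a gas would meet the positive-deficit reading assumes only that a deficit of -12 or lower is very rare. That the composite would then be uninformative assumes that any one component counts. No effect on a relative risk is claimed, because the documents give no rates from which to work one out.

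**What to change.** Rewrite the component in Section 1.2 item g and Section 3.2 item h.c to match Section 4.8.2 item p.c: arterial cord base deficit above 12, equivalently base excess below -12. Add one line, in Section 4.8.3 or the abstraction instructions, stating that deficit is recorded as a positive number and that a value charted as base excess has its sign reversed before the rule is applied. Correcting Section 3.2 alone would leave the stored-sign slip open.

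The cost is a wording change in two places and one added sentence. No new threshold is introduced, and sample size and trial conduct do not change.
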